### **10.3 Data Transformations**

No transformations have been identified for the analysis of the primary and secondary endpoints.

### **10.4 Multicentre Studies**

This is a single-site study.

### **10.5 Multiple Testing**

The power of this trial is based on a single analysis that focus only on the primary endpoint. The remaining secondary analyses will be considered exploratory and hypothesis generation and therefore no methods will be used to preserve the overall significance level (as in multiple testing procedures).

### **10.6 Planned Subgroups, Interactions, and Covariates**

No subgroup or interaction analyses are planned.

## **11 Study Subjects**

### **11.1 Subject Disposition**

SCOPE-BD NUIG-2017-002, Statistical Analysis Plan Version 1, 19/03/2024

Different variables from the CRF will be considered to determine the number of patients who reached the various stages of the study. Summaries will be presented as the number and percentage of patients who are initially screened (Visit 1), enrolled for the run-in period, attend for initial treatment visit (Visit 3), satisfy the run-in criteria, receive initial treatment (IV at Visit 3) and attend for the subsequent treatment visits (Visits 4 & 5) and follow-up visits in the study.

## 11.2 Protocol Deviations

Protocol deviations include:

- There are any issues with the informed consent (consent not obtained or obtained after study procedures started).
- The inclusion /exclusion criteria are not followed correctly.

In the unlikely case that any deviations occur, a brief explanation will be presented in the clinical study report.

## 11.3 Inclusion and Exclusion Criteria

The number and percentage will be presented for subjects meeting each of the Inclusion and Exclusion Criteria in the trial sample, post run-in phase. It is expected that the overall percentage will be 100% for inclusion and exclusion criteria, except when waivers are granted or when data review indicates that inclusion or exclusion criteria have been violated.

# 12 Demographic and Baseline variables

## 12.1 Demographics

The following will be considered demographic variables: Age, Gender, Race and handedness. Handedness will be accurately measured utilising the Modified Edinburgh Handedness Inventory (MEHI). Mean, standard deviation, median, max and min will be reported for continuous variables, and counts and percentages will be reported for categorical variables. These variables will be summarised by treatment group.

## 12.2 Prior and Concurrent medications

Concomitant medications are recorded in the Concomitant Medications Form of the CRF. For each one of the generic names, summaries will be provided for the number of times the medication was reported at baseline (counts and percentages), the number of times the medication was added during the treatment period (counts and percentages).

## 12.3 Baseline and Screening Conditions

SCOPE-BD NUIG-2017-002, Statistical Analysis Plan Version 1, 19/03/2024

All outcome variables (primary and secondary) at baseline, and additional baseline variables including smoking, alcohol and drug usage, medical/surgical history, clinical history of bipolar disorder, NEO-PI diagnosis and WAIS scores (Verbal/Performance/Total) will be summarised for each treatment group using descriptive statistics.

## 12.4 Treatment Compliance

Treatment will be summarised by reporting the number and percentage of participants who attend and receive IV (placebo or Scopolamine) for each treatment Visit 3, 4 and 5. The numbers and percentages of eligible trial participants will also be summarised by total number of IV treatments received (0, 1, 2 or 3 IV treatments). This total IV treatments received variable will be used in efficacy analysis to explore the impact of receiving IV treatments, in addition to being randomised to them.

# 13 Efficacy Analyses

## 13.1 Primary Efficacy Analysis

For the primary effectiveness analysis of the primary outcome, it is expected that pre-randomisation measurements of the HDRS score will be correlated with the scores obtained at Visit 6 of treatment. The mean scores at Visit 6 will be compared across the study arms using an ANCOVA model. The response variable will be the change in HDRS score from Visit 3 to HDRS at Visit 6 including the HDRS score at Visit 3 as a covariate in the model.

The addition of stratifying variables and other variables as covariates will be considered as appropriate. This analysis will increase the power to detect significant differences between the groups.

Inverse probability weighting will be applied to the primary outcome analysis. These weights will be derived based on the inverse of the probability of a patient's data being missing given their pre-randomisation measurements. This will ensure the estimate and inference is more representative of all patients randomised, reducing bias in the estimation of the treatment effect due to participants lost to follow-up and missing data.

Inference regarding the treatment effectiveness will focus on the point estimate, confidence interval and p-value for hypothesis confirmation.

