Mode of administration	15 minutes IV infusion

Placebo	Saline (Sodium Chloride 0.9%)
Dose	100 ml
Mode of administration	15 minutes IV infusion
Duration of treatment	Run-in period will be a maximum 21 days. The treatment period will be a maximum 10 days and the maximum number of days for follow up is 28 days
Primary endpoint	The primary endpoint will be the change in severity of objective depressive symptoms as measured by change in HDRS score from pre-randomisation (pre-IV infusion at Visit 3) compared to Visit 6.
Secondary endpoints	These include change in severity of depressive symptoms at study Visits 3, 4, 5, 6 and 7 and changes in cognitive scores at Visit 6
Statistical methods	The primary analysis of the primary outcome will estimate the difference in change in HDRS score between groups from pre-randomisation (pre-IV on Visit 3) to Visit 6 (with treating scores as continuous variables). Secondary outcomes will be analysed as appropriate to the distribution of each outcome, comparing the difference between groups at the specified follow-up visits. Pre-randomisation variables predictive of each outcome; and stratifying variables will be included in ANCOVA or generalised linear models of outcome variables. Inverse probability weighting will be used to account for missing outcome data and loss to follow-up at a given follow-up visit.

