11.8 Procedure for accounting for missing, unused and spurious data

Any missing data which occurs will be summarised and reasons given. As per the statistical analysis specification, an inverse probability weighting will be performed in the primary outcome analysis (weights based on the inverse probability of a patient's data being missing

given their pre-randomisation measurements). This will ensure the estimate and inference is more representative of all patients randomised.

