11.9 Procedure for reporting any deviation(s) from the original statistical plan

Deviations from the original statistical plan will be recorded and justified in the final report.

12. Direct Access to Source Data/Documents

Direct access will be granted to authorised representatives from the sponsor, and the regulatory authorities to permit trial-related monitoring, audits and inspections. Consent from patients/legal representatives for direct access to data will also be obtained. The patients' confidentiality will be maintained and will not be made publicly available to the extent permitted by the applicable laws and regulations.

13. Data handling and record keeping

Data will be entered, handled and stored at the HRB-CRFG. It will be pseudo-anonymised and then processed by members of the research team at the HRB-CRFG. Data will also be submitted to a data repository at the National Institute of Mental Health (NIMH) based in Maryland, Bethesda, USA on a twice-yearly basis to house data on behalf of SMRI.

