## **10 General issues for Statistical Analysis**

### **10.1 Software used for the analysis**

All the statistical analyses will be carried out in R statistical software (version 3.6.0 or higher) unless otherwise noted by the statisticians assigned to this study. Primary and secondary analysis will be reviewed by an independent statistician, and all the code generated will be kept by the study statistician.

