### **10.2 Methods for Withdrawals, Missing Data, and Outliers**

Any missing data which occurs will be summarised and reasons given. As per the statistical analysis specification, an inverse probability weighting will be performed in the primary outcome analysis (weights based on the inverse probability of a patient's data being missing given their pre-randomisation measurements). This will ensure the estimate and inference is more representative of all patients randomised.

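### The primary-analysis weights are defined as the inverse of the probability of being missing, which works against their stated aim of representing everyone randomised

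*SAP*

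**What the plan says.** SAP 13.1 specifies an ANCOVA of change in HDRS from Visit 3 to Visit 6, with Visit 3 HDRS as covariate and inverse probability weighting. It defines the weights thus: "These weights will be derived based on the inverse of the probability of a patient's data being missing given their pre-randomisation measurements". The next sentence gives the purpose: "This will ensure the estimate and inference is more representative of all patients randomised, reducing bias in the estimation of the treatment effect".

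The same definition stands in three other places:

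- SAP 10.2: "weights based on the inverse probability of a patient's data being missing given their pre-randomisation measurements".
- Protocol 11.5.1, in the same words as SAP 13.1.
- Protocol 11.8: "weights based on the inverse probability of a patient's data being missing".

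All four sections state the aim of representing all patients randomised. The protocol synopsis (Statistical methods) names the method without defining a weight: "Inverse probability weighting will be used to account for missing outcome data and loss to follow-up at a given follow-up visit". No section refers to the probability that the outcome is observed. SAP 9 limits the effectiveness analysis to randomised participants with follow-up data, so only patients with a Visit 6 HDRS can carry a weight.

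**The concern.** A weight can be applied only to a patient whose outcome was seen. For those patients to stand in for everyone randomised, each must count in proportion to the inverse of the probability of being seen. The documents invert the opposite probability. The completers most like the dropouts, who should be weighted up, are then weighted down, and the adjustment moves the analysed sample further from the randomised population than no weighting would.

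This rule produces the trial's only confirmatory estimate, confidence interval and p-value (SAP 13.1; protocol 11.7). With 50 randomised and about 6 expected to be missing, a few extreme weights can matter.

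**Working it through.** **The plan's own figure.** SAP 7 gives 85% power with 22 per arm for a difference of 12, SD 13, two-sided alpha 0.05. The exact t-test power is 84.9%, and 44/(1 - 0.12) = 50. The figure reproduces and does not depend on the weights.

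**Which weight meets the aim.** Let f(x) be the share of randomised patients with baseline x and π(x) the probability that their Visit 6 HDRS is observed. Completers with baseline x occur in proportion to f(x)π(x), and after weighting to w(x)f(x)π(x). This returns f(x) only if w is proportional to 1/π(x). With w = 1/(1 - π(x)), the weighted sample is f(x) multiplied by the odds of being observed, which tilts it away from the dropouts.

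**Single weights.**

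| P(missing) | 1/P(missing), as written | 1/P(observed) |
|---|---|---|
| 0.05 | 20 | 1.05 |
| 0.12 | 8.33 | 1.14 |
| 0.30 | 3.33 | 1.43 |

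As written, the patient least like a dropout counts 20/3.33 = 6 times as much as the one most like a dropout.

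**Worked example** (strata sizes and rates assumed; 6 of 50 missing as in SAP 7). Randomise 25 severe and 25 mild-moderate patients, with 20% and 4% missing, leaving 20 and 24 completers.

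- Target severe share: 50%.
- Unweighted: 20/44 = 45.5%.
- As written, weights 1/0.20 = 5 and 1/0.04 = 25: 100/(100 + 600) = 14.3%. Effective sample size: 700²/(20×25 + 24×625) = 31.6 of 44.
- Corrected, weights 1.25 and 1.04: 25/(25 + 25) = 50%. Effective sample size: 43.6.

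At 16%/8% missing, the severe share as written is 31.3%; at 4%/20% it is 85.7%; at 12%/12% it is 50%. The corrected weight gives 50% each time.

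**Simulation of the weighted ANCOVA.** From SAP 7: N = 50, baseline mean 24, effect -12, 12% missing. Assumed: baseline SD 5, residual SD 6, slope 0.5, and logistic missingness on baseline HDRS with odds ratio (OR) per SD as shown. There were 4,000 trials per scenario. Fitted weights come from a logistic regression on baseline HDRS.

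Constant treatment effect: SD of the estimate, as written vs corrected.

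| OR | Known weights | Rise | Fitted weights | Rise |
|---|---|---|---|---|
| 1.0 | 1.82 vs 1.82 | 0% | 2.03 vs 1.82 | 12% |
| 1.5 | 1.96 vs 1.84 | 7% | 2.24 vs 1.84 | 22% |
| 2.0 | 2.16 vs 1.86 | 16% | 2.43 vs 1.87 | 30% |
| 3.3 | 2.66 vs 1.82 | 46% | 2.93 vs 1.83 | 60% |

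There is no bias in these scenarios. With known weights as written, the effective sample is 100%, 88%, 69% and 39% of completers. The fitted figures at the two larger odds ratios are approximate: repeat runs gave 2.43 to 2.83 at OR 2.0 and 2.93 to 3.24 at OR 3.3.

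Effect varying with baseline (true mean -12, known weights as written): mean estimate for each sign of the variation.

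| OR | 0.25 points per HDRS point | 0.5 points per HDRS point |
|---|---|---|
| 1.5 | -11.6 or -12.4 | -11.1 or -12.9 |
| 2.0 | -11.2 or -12.7 | -10.5 or -13.5 |
| 3.3 | -10.8 or -13.2 | -9.6 or -14.3 |

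In the same scenarios unweighted ANCOVA stays between about -11.7 and -12.3, and 1/P(observed) between -11.9 and -12.1.

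**The case against.** **The intent can be recovered.** The method is named, its aim is stated, and the text says the weights are based on this probability, which leaves room for 1/(1 - P(missing)). A competent statistician would probably program the right weight, and SAP 10.1 adds a check: "Primary and secondary analysis will be reviewed by an independent statistician". This is fair, and it makes literal programming less likely. It does not correct a text that names the wrong probability in all four places that define the weight. A reviewer who checks code against the SAP has no correct definition to check against. An analyst who uses the right weight departs from the written plan, and protocol 11.9 applies: "Deviations from the original statistical plan will be recorded and justified in the final report".

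**The harm is conditional.** Bias needs literal programming, dropout that depends on baseline, and an effect that varies with the same variables. The documents give no evidence for the last two, and OR 3.3 with 0.5 per point is extreme. This stands: the bias figures show what could happen and are not a forecast.

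**The residual SD is optimistic.** The assumed change-score SD is √(6² + (0.5×5)²) = 6.5, half the planning SD of 13. In the worst constant-effect case, 12/2.93 is still more than 4 SDs from zero. This also stands, but the document's own SD makes matters worse. With a constant effect the SD of the estimate scales with the residual SD, so a residual SD of 12 gives about 2×2.93 = 5.9 as written against 2×1.83 = 3.7 corrected. An effect of -12 is then about 2.0 against 3.3 SDs from zero. In addition, at OR 3.3 with fitted weights as written, the model-based 95% interval covered the true effect only about 79% of the time.

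**Conclusion.** The weight is wrong as written, and this does not depend on any assumption: 1/P(missing) cannot meet the aim that the same sections state, unless missingness is unrelated to baseline.

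The size of the consequence does rest on assumptions, first of all that the text is programmed literally. If dropout is unrelated to baseline, known weights do no harm, and fitted weights cost about 12% in the SD of the estimate. If dropout depends on baseline and the effect is constant, the cost is precision: 22% to 60% with fitted weights for odds ratios of 1.5 to 3.3. If the effect also varies with baseline by 0.25 points per HDRS point, the estimate shifts by about 0.4 to 1.2 points in either direction, more than with no weights. Because the rule governs the only confirmatory analysis and is cheap to correct, it should be corrected before the analysis is run.

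**What to change.** In SAP 10.2 and 13.1, define the weight as 1 / P(Visit 6 HDRS observed | pre-randomisation measurements), applied to participants with an observed Visit 6 HDRS. Make the same change in protocol 11.5.1 and 11.8 at the next amendment, or record the correction under protocol 11.9.

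Two additions are useful but separate from the error:

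- State the standard error. A robust (sandwich) form is the usual choice with weights, and its small-sample version should be named. In the constant-effect simulation with corrected weights, coverage was about 94% with an uncorrected sandwich and 95% with the model-based error, so little turns on it here.
- Use the Visit 6 contrast from the mixed model already planned in SAP 13.2 as a sensitivity analysis for missing data.

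The cost is a wording change in two SAP sections, plus two matching protocol sections or a recorded deviation. It needs no new data and no new patients.

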8.3.5 Treatment (Visit 3, Visit 4 and Visit 5)

At Visit 3, after assessment, participants will be randomised to placebo (n=25) (100mls IV Saline) or 4 µg/kg Scopolamine (n=25) IV in 100mls of Saline over 15 minutes and receive further infusions at Visits 4 (days 2-6) and 5 (days 6-10), with at least 2 days between IV infusions (see Table 2).

Assessments at Visits 3 prior to randomisation to ensure trial eligibility

- As per inclusion criterion 7 and exclusion criteria 21 and 22.
- HDRS ≥ 8 (indicating depressed mood of at least mild severity)
- YMRS <6 (indicating patient is not (hypo)manic)
- Medication review to ensure no participants have been prescribed medications which would exclude the participant from the trial between Visit 2 and Randomisation.
- Confirmation of pregnancy serum result (females only)

Randomisation via Interactive Web Response System (IWRS) (Visit 3 only)

Assessments at Visits 3, 4 and 5 are:

- Review of any medication changes
- Vital Signs recorded (BP, HR, RR) (pre-infusion but post cannulation)

- Dispensing via IWRS (Visit 3, 4, and 5)
- Completion of HDRS questionnaire (Visit 3 (completed as part of eligibility assessment), Visit 4, and 5, pre-infusion)
- Completion of MADRS questionnaire (Visits 3, 4 and 5, pre-infusion)
- Completion of YMRS (Visit 3 (completed as part of eligibility assessment), Visit 4, and 5, pre-infusion)
- Confirmation of pregnancy status (Urine dipstick) and contraception advice (Visit 3, 4 and 5, pre-infusion)
- Completion by participant of VAS (Visit 3, 4, and 5, pre-infusion)
- Completion by participant of the POMS (Visit 3, 4, and 5, pre-infusion) (optional)
- Completion of GAF questionnaire (Visits 3 and 5, pre-infusion)
- Completion of CGI-S (Visit 3, 4 and 5, pre-infusion)
- Completion of CGI-I (Visits 3, 4 and 5, pre-infusion)
- IV cannulation
- Cannulation site check (pre-infusion and post-infusion)
- Completion by participant of the POMS (minimum 15 minutes post-infusion (optional)
- Completion by participant of VAS (minimum 15 minutes post-infusion)
- Completion by participant of CANTAB subscales (Visit 3, post-infusion) (optional)
- Completion of WAIS (post infusion at Visit 3, 4, or 5) (optional)
- Completion of NEOPI-FFI (post infusion at Visit 3, 4, or 5) (optional)
- Vital Signs recorded (BP, HR, RR) (within 15 minutes of infusion stopping and 50 to 90 minutes post-infusion)
- Completion by participant of the PRISE questionnaire (post-infusion at Visit 3, 4 or 5 optional)

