8.11 Discontinuation/withdrawal of participants from study protocol

Study participants have the right to voluntarily discontinue study treatment or withdraw from the study at any time for any reason without any consequences.

The investigator has the right to discontinue a participant from study treatment or withdraw a participant from the study at any time if it is in the best interest of the participant. In this instance, participants must discontinue the investigational medicinal product (Scopolamine) and be withdrawn from the study. Reasons for investigator to discontinue a participant from study treatment include but are not limited to:

- Pregnancy,
- Involuntary detention under the MHA 2001 in an acute psychiatric inpatient unit
- Treatment with ECT
- Severity of symptoms such that participation in a clinical trial is not appropriate because of the risk of imminent self-harm (based on review by clinician at study visit)
- Development in the study of narrow angle glaucoma, myasthenia gravis, paralytic ileus, pyloric stenosis, toxic megacolon and acute porphyria.
- Development post-infusion of bradycardia (HR < 50 bpm), tachycardia (HR > 100bpm) or hypotension (Systolic BP <90mm HG or Diastolic BP <60mm Hg) that required clinical treatment (e.g. administration of additional medications, review in Emergency Department)
- Treatment at day of infusion with anticholinergic medications (e.g. Physostigmine, Biperiden, Procyclidine)

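### The missing-data weights use baseline data only, so they do nothing about dropout that follows the early HDRS course; the Visit 4 and 5 HDRS should be used

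*SAP*

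**What the plan says.** SAP 13.1 fits an ANCOVA: "The response variable will be the change in HDRS score from Visit 3 to HDRS at Visit 6", with Visit 3 HDRS as a covariate. It then adds weights, taken as the inverse of the probability of "a patient's data being missing given their pre-randomisation measurements". SAP 10.2 repeats this ("weights based on the inverse probability of a patient's data being missing given their pre-randomisation measurements"), and protocol 11.5.1 and 11.8 use the same basis. No list of variables for the weight model is given. SAP 13.1 states the purpose as "reducing bias in the estimation of the treatment effect due to participants lost to follow-up and missing data".

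Allocation takes place at Visit 3, after the HDRS and YMRS (protocol 8.6, SAP 6.3). A model confined to measurements made before randomisation therefore contains neither arm nor anything later. Yet HDRS is scheduled before the second and third infusions (protocol 8.3.5): "Completion of HDRS questionnaire (Visit 3 (completed as part of eligibility assessment), Visit 4, and 5, pre-infusion".

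Two other planned analyses bear on this. SAP 13.2 has a mixed-effects model of the HDRS time course with arm, visit and their interaction, described as an additional analysis. SAP 13.3 has sensitivity analyses, but these concern the number of infusions received, not missing outcomes.

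**The concern.** Weights correct for selective loss only through the variables in the weight model. Visit 3 HDRS is already in the ANCOVA, so weighting on it again mostly repeats an adjustment that the outcome model makes. Loss that depends on what happens after Visit 3 is left alone.

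Most reasons for stopping listed in protocol 8.11 arise after randomisation. One is "Severity of symptoms such that participation in a clinical trial is not appropriate because of the risk of imminent self-harm"; others are ECT, involuntary detention and treated haemodynamic reactions after an infusion. Participants may also decline further infusions (protocol 9.6). Several of these could follow the early HDRS course, and could do so differently in the two arms. If so, the confirmatory estimate and p-value come from an analysis whose stated protection does not act on that loss, while the HDRS scores that could help go unused.

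**Working it through.** **Inputs from the documents.** Two-sided two-sample t-test, alpha 0.05, difference 12, SD 13 (plausible range 5 to 13), 22 evaluable per arm, 50 randomised, 6 missing at Visit 6, mean baseline HDRS 24 (SAP 7).

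**The plan's own figures.**
- Standard error of the difference: 13 × √(2/22) = 3.92.
- Power, normal approximation: Φ(12/3.92 − 1.96) = Φ(1.10) = 86.5%. The exact t-test gives 84.9%. The stated 85% is reproduced.
- 44/(1 − 0.12) = 50, so the planned loss is 12%.

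**Assumptions not in the documents.** Equal correlation between visits of 0.5 or 0.7. Half of the effect present at Visit 4 and 80% at Visit 5. Logistic dropout on the Visit 3-to-5 HDRS change, with log-odds 1 to 1.5 per SD. For contrast, dropout on arm alone and on arm × baseline was also run. All computed weights are one over the probability of being observed; whether the SAP's wording says that is a separate point.

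**Large-sample check.** 400,000 participants per scenario, 12% missing at Visit 6, planned ANCOVA. The table shows SD 13 and correlation 0.5. Entries are bias in the scopolamine-minus-placebo difference in HDRS units; positive means the benefit is understated. The last column uses weights on arm, Visit 3, 4 and 5 HDRS and arm interactions.

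| Who tends to be lost | True effect | No weights | Baseline only | Baseline + arm | Arm + Visits 3–5 |
|---|---|---|---|---|---|
| Scopolamine responders, placebo non-responders | 12 | 0.73 | 0.73 | 0.73 | 0.02 |
| Same | 0 | 0.73 | 0.73 | 0.73 | 0.01 |
| Scopolamine non-responders, placebo responders | 12 | −0.66 | −0.66 | −0.66 | 0.05 |
| Placebo non-responders only | 12 | 0.53 | 0.54 | 0.54 | −0.04 |
| Non-responders in both arms | 12 | 0.15 | 0.15 | 0.15 | −0.04 |
| Non-responders in both arms | 0 | 0.03 | 0.03 | 0.03 | 0.03 |
| Depends on arm only | 12 | −0.01 | −0.01 | −0.01 | −0.01 |
| Depends on arm × baseline | 12 | 0.01 | 0.01 | 0.01 | 0.00 |

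Three things follow.
1. Baseline-only weights equal no weights, within 0.01 unit, whenever loss follows early change.
2. Adding arm alone changes nothing, and loss that depends on arm or on arm × baseline causes no bias, because the ANCOVA already contains both.
3. With a true effect of 12 and loss that follows early change, the absolute bias over both correlations was 0.15 to 0.73 at SD 13 and 0.16 to 0.26 at SD 5.

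**Check at the trial's size.** n = 50, 12% missing, SD 13, correlation 0.5, true effect 6, log-odds 1.2 per SD of change, Visit 5 HDRS known for everyone, 4,000 runs, probabilities truncated at 0.02. Opposite-direction loss (first row of the table):
- Baseline-only weights: bias 0.89, root mean squared error (RMSE) 3.53. The Monte Carlo error of the bias is about 3.53/√4,000 = 0.06.
- Weights on arm, Visit 3 HDRS, Visit 5 HDRS and arm × Visit 5 HDRS: bias 0.51, RMSE 3.52. Between 12% and 17% of runs were close to separation.
- Same-direction loss: RMSE rose from 3.47 to 3.60 with that richer weight model.

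That model removed at best about half the bias even with 100,000 participants. It lets only the later score interact with arm, so it cannot represent arm-specific loss driven by change. In a further run at n = 50, baseline-only weights again matched complete cases within about 0.02. Regression imputation from the Visit 4 and 5 HDRS, standing in for a likelihood or multiple-imputation analysis, removed essentially all the bias at similar precision (for example RMSE 3.45 against 3.52).

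**Size.** 0.73/3.92 = 0.19 and 0.89/3.92 = 0.23 of a standard error. 0.73/12 is 6% of the planned difference.

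**The case against.** The largest figures need placebo participants to leave when worse and scopolamine participants to leave when better. The mood-related reasons in protocol 8.11 all point to leaving when worse. In that same-direction case the bias is small, it understates the benefit, and it vanishes when there is no effect, so it does not inflate the type I error. This stands. Even so, loss that follows the course in the placebo arm alone gave about 0.5 units without anyone leaving because of improvement, and the list in 8.11 is not exhaustive.

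The documents also limit the problem. Stopping infusions is not the same as losing Visit 6: protocol 8.7, 8.11 and 9.8.2 ask for continued assessment, and Visit 6 may be done by telephone (8.3.6). Follow-up after discontinuation is, however, an aim and not assured. The mixed model in SAP 13.2 uses the Visit 4 and 5 HDRS, but it is neither the primary analysis nor named as the analysis for missing data.

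The SAP claims reduced bias, not its removal, and weights on other baseline variables could help with loss that depends on those. That is fair. The claim fails only for loss that follows the post-randomisation course.

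A reader might infer three stronger things that the material does not support:
- That leaving arm out of the weights is itself a source of bias. It is not, as the table shows.
- That loss from side effects must bias the result. It does so only if it is related to Visit 6 HDRS given arm and baseline. Adding HDRS to the weights would cover it only as far as HDRS and arm explain it.
- That putting the Visit 4 and 5 HDRS into the weights removes the bias in general. At n = 50 it did not.

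**Conclusion.** The point holds in a limited form. As specified, the weights act on nothing that happens after Visit 3, so the bias reduction that SAP 13.1 claims is not delivered for dropout that follows the early HDRS course.

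At 12% loss and SD 13 the bias is up to about 0.7 to 0.9 units if the mechanism differs by arm. If it is the same in both arms, the bias is about 0.2 with a true effect and about zero without one. That is at most about a quarter of a standard error and would rarely change the conclusion alone. It would grow with heavier loss: a separate simulation with decaying correlation and a true effect of 6 gave estimates of 5.25 at 12% and 4.9 at 20%, a bias of 0.75 and 1.1.

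The absence of any effect from baseline-only weights does not depend on a particular scenario. The sizes do: they rest on assumed correlations, timing of effect and dropout mechanisms, none of which the documents give.

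**What to change.** Bring the Visit 4 and 5 HDRS into the handling of missing Visit 6 data, and amend SAP 10.2 and 13.1 and protocol 11.5.1 and 11.8 to match, before unblinding.

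- **Preferred.** Specify the SAP 13.2 model fully: visit × arm, Visit 3 HDRS as covariate, a stated covariance structure, and the Visit 6 contrast as the estimate. Alternatively, use multiple imputation by arm from the Visit 3 to 5 HDRS. Name one of these as the primary missing-data method, or as the missing-data sensitivity analysis for the primary endpoint.
- **If weighting is kept.** Model the probability that Visit 6 HDRS is observed on a short pre-specified list: arm, latest available HDRS change from Visit 3, and their interaction. Truncate the weights at a stated value. Say openly that with about 6 missing values such weights are unstable and may correct the bias only partly.
- **If neither is adopted.** Remove the bias-reduction claim.

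The cost is wording and programming; no new data are needed. None of these options helps with a participant who leaves before Visit 4, because no post-randomisation HDRS then exists. The report should therefore show missing Visit 6 data by arm, last HDRS and reason.
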